### **Research plan**

#### **1. Research content**

Pregnant women diagnosed with normal-high TSH and positive TPOAb before 20 weeks of pregnancy who received perinatal care and gave birth in the Third Affiliated Hospital of Zhengzhou University from July 2019 to October 2023 were selected and divided into two groups, A and B, with 100 cases in each group according to the dose of LT4 of 25ug and 50ug; those who did not take LT4 were group C, with 200 cases. The clinical efficacy of different doses of LT4 in the treatment of pregnant women with normal-high TSH and positive TPOAb in the first half of pregnancy was explored.

Inclusion criteria: (1) Diagnosed with normal-high TSH and positive TPOAb before 20 weeks of pregnancy (TSH: 2.5mIU/L-upper limit of reference range, TPOAb  $>$  34IU/mL), FT4 in the normal range (FT4: 12-22pmol/L) in line with the diagnostic criteria established by the Laboratory Department of the Third Affiliated Hospital of Zhengzhou University; (2) All subjects voluntarily participated and signed informed consent

Exclusion criteria: (1) Multiple pregnancy (2) Assisted reproductive technology; (3) Suffering from

serious diseases or diseases that affect pregnancy outcomes, such as dysfunction of important organs; (4) Suffering from thyroid disease; (5) Diagnosed with a history of other endocrine, antiphospholipid syndrome and other autoimmune diseases; (6) Taking drugs that affect the thyroid gland (7) LT4 allergy

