## 2. Research steps

- ① Select pregnant women who meet the inclusion and exclusion criteria and group them, and record the basic information of the pregnant women, mainly including: age, height, weight, pregnancy and delivery history, thyroid function and other serological indicators.
- ② Collect blood and stool samples from pregnant women in groups A and B before and after LT4 treatment, track thyroid function indicators such as TSH, FT4, TPOAb before and after treatment in the three groups of pregnant women, and record maternal and fetal nutritional development.
- ③ Pregnancy outcomes: Track and follow up maternal and fetal outcomes, including the incidence and mode of delivery of adverse pregnancy outcomes such as miscarriage, premature birth, gestational hypertension, gestational diabetes, premature rupture of membranes, fetal growth restriction, macrosomia, intrapartum blood loss, neonatal sex, weight, head circumference, height, Apgar score, thyroid disease, etc.
- ④ Statistical methods: SPSS 26.0 software was used for statistical analysis; continuous data were described by (mean  $\pm$  standard deviation), and count data were expressed by frequency and rate; two independent samples that met normal distribution and homogeneity of variance were analyzed by t test and corrected t test; comparison of binary data between two independent samples of count data was analyzed by X test and corrected X test; P < 0.05 was considered statistically significant.

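### Groups are formed by LT4 taken, with no index date, so the miscarriage comparison of LT4 with no LT4 is open to immortal time bias favouring LT4

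*Combined protocol and SAP*

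**What the plan says.** Section 1 (Research content) draws its population from women "diagnosed with normal-high TSH and positive TPOAb before 20 weeks of pregnancy" and "who received perinatal care and gave birth in the Third Affiliated Hospital of Zhengzhou University from July 2019 to October 2023". It divides the treated women into A and B, "with 100 cases in each group according to the dose of LT4 of 25ug and 50ug"; the comparator is "those who did not take LT4 were group C, with 200 cases". It mentions no randomisation, assignment date, start of follow-up, or permitted gap between diagnosis and first dose.

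Section 2 (Research steps) adds four points:
- Item 1: "Select pregnant women who meet the inclusion and exclusion criteria and group them". When this happens relative to the first dose is not stated.
- Item 2: "Collect blood and stool samples from pregnant women in groups A and B before and after LT4 treatment".
- Item 3 follows pregnancy outcomes, "including the incidence and mode of delivery of adverse pregnancy outcomes such as miscarriage", with no risk window.
- Item 4: "comparison of binary data between two independent samples of count data was analyzed by" a chi-square or corrected chi-square test. No landmark, time-dependent exposure or adjustment is mentioned.

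**The concern.** Eligibility is met at diagnosis, but the only stated grouping rule is what was taken afterwards. If LT4 starts some days or weeks after diagnosis, a woman must still be pregnant on the starting day to enter A or B. A woman whose pregnancy ended before that day did not take LT4, so she is counted in C or leaves the analysis. The LT4 groups therefore carry a stretch of time in which no loss can be counted against them. A chi-square test on proportions does not correct this, and neither would adjustment for baseline covariates.

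A second weakness is that women may be diagnosed at any time before 20 weeks. Early entrants have more time at risk of miscarriage than late ones, and a comparison of crude proportions ignores the difference. The direction of this effect is unknown.

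At stake is the LT4 v no-LT4 contrast for miscarriage, which is the first pregnancy outcome listed and one of the harms that the background gives as a reason for treatment. The 25 v 50 ug contrast is affected only if the delay to first dose, or changes of dose, differ between A and B.

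**Working it through.** The plan gives no event rate, delay or power calculation, so there is no stated figure to reproduce. What follows illustrates size only.

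**From the plan:** A = 100, B = 100, C = 200; significance at P < 0.05 (two-sided assumed).

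**Assumed:** no LT4 effect; N = 200 women destined for LT4 and N = 200 not; 10% loss after diagnosis, so L = 20 per side; a fraction f of the LT4 women's losses falls before the first dose (f = 0.1, 0.2, 0.3).

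**Case 1: pre-dose losses move to C.** LT4 rate = (L - fL)/(N - fL); C rate = (L + fL)/(N + fL).
- f = 0.1: 18/198 = 9.1% v 22/202 = 10.9%, RR 0.83
- f = 0.2: 16/196 = 8.2% v 24/204 = 11.8%, RR 0.69
- f = 0.3: 14/194 = 7.2% v 26/206 = 12.6%, RR 0.57

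**Case 2: pre-dose losses are only dropped.** The LT4 rate is unchanged; C stays at 20/200 = 10.0%.
- f = 0.1: RR 0.91
- f = 0.2: RR 0.82
- f = 0.3: RR 0.72

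**Chance of a significant result favouring LT4** (nominal 2.5%). By normal approximation it is Φ[(difference - 1.96 × SE0)/SE1], where SE0 is the pooled and SE1 the unpooled standard error of the difference. Worked for case 1, f = 0.1: difference 0.0180, both SEs 0.0300, so Φ(0.60 - 1.96) = Φ(-1.36) = 8.7%.
- Case 1: about 9%, 22% and 44%
- Case 2: about 5%, 9% and 16%

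**Second check, in terms of delay.** Assume a constant hazard over 10 weeks after diagnosis, total risk p = 10%, half the women destined for LT4, first dose d weeks after diagnosis, and pre-dose losses moved to C. Let h = -ln(1 - p)/10 and q = 1 - exp(-hd). Then LT4 rate = (p - q)/(1 - q) and C rate = (p + q)/(1 + q).
- d = 0: RR 1.00
- d = 1 (q = 0.0105): 9.0% v 10.9%, RR 0.83; false finding for LT4 9% (A+B v C) or 7% (one dose group v C)
- d = 2: 8.1% v 11.8%, RR 0.68; 24% or 15%

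The RR hardly moves for p between 3% and 15% (0.82-0.83 at one week, 0.67-0.69 at two). It does depend on the share destined for LT4: at p = 10% and d = 2 it is 0.75 if that share is 30% and 0.57 if it is 70%.

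**The delivery restriction.** Section 1 selects women who gave birth at the hospital; section 2, item 3 reports miscarriage. Taken literally, the first makes every miscarriage rate zero, so this bias could not appear in that outcome, but the outcome could not be estimated either. The two statements cannot both stand.

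**The case against.** A reader might infer that the plan counts miscarriage from diagnosis and groups by whether LT4 was ever taken, so that pre-dose losses necessarily land in C and LT4 is bound to look protective. The documents do not support that.
- They state neither a start of follow-up nor an exposure window.
- Items 1 and 2 of the Research steps can be read as grouping at enrolment: women are selected and grouped, then A and B are sampled before and after LT4. On that reading a pre-dose loss stays in A or B, or drops out for want of a second sample; it does not move to C.
- If LT4 started on the day of diagnosis, there is no bias.
- If only deliveries were included, no miscarriage is analysed.

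Nor does the whole comparison have a known direction. The background and safety sections tie LT4 to early pregnancy. If treated women entered earlier, they carried more miscarriage risk time, which works against LT4.

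The reach is also limited. The stated purpose is a comparison of doses, miscarriage is one item in a long list, and no primary outcome is named.

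These points stand and restrict the claim to an open risk. They do not remove it: the only written grouping rule is LT4 taken, nothing fixes it at a date before dosing, and the planned test would not correct the error if it occurred.

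**Conclusion.** The concern holds as a gap in the design that leaves the LT4 v no-LT4 miscarriage comparison open to immortal time bias. That bias favours LT4 whether pre-dose losses are moved to C or dropped. Under the stated assumptions the spurious RR lies between 0.91 and 0.57, and the chance of a false finding for LT4 between about 5% and 44%, against a nominal 2.5%. The lower end applies if losses are only dropped and few precede dosing; the upper end if they move to C and many do. The loss rate, the delay and the share destined for LT4 are not in the documents, so the actual size may be anything down to nil. Unequal gestational age at entry adds an error of unknown direction. Separately, the restriction to women who delivered contradicts the miscarriage outcome and must be settled first.

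**What to change.** 1. Reconcile the delivery restriction with the miscarriage outcome: define the cohort as all eligible women from diagnosis, whatever the outcome of the pregnancy.
2. For miscarriage, replace the chi-square test with a Cox model on the gestational-age scale, with delayed entry at diagnosis and LT4 (25 ug, 50 ug) as a time-varying exposure from the first-dose date. Time and losses before the first dose then count as untreated, and women are compared at the same gestational age. Report A-C and B-C hazard ratios with 95% CI, and the distribution of delay from diagnosis to first dose.
3. If groups were in fact assigned at enrolment before dosing, state this and analyse by assigned group from that date.

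A landmark at matched index weeks is not an equivalent substitute, because C can still contain intended LT4 users lost before dosing. In simulations with no LT4 effect (for example entry at weeks 6-16, declining hazard, delays of up to three weeks) it left an RR of about 0.91-0.97, against about 1.00 with time-varying LT4. It can serve as an approximate sensitivity analysis.

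Cost: diagnosis, first-dose and loss dates from the antenatal record, some extra analysis, and possibly a slightly wider interval. Treatment does not change. The model removes the timing error only; confounding between women who did and did not take LT4 is a separate matter.

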## 2. Research steps

- ① Select pregnant women who meet the inclusion and exclusion criteria and group them, and record the basic information of the pregnant women, mainly including: age, height, weight, pregnancy and delivery history, thyroid function and other serological indicators.
- ② Collect blood and stool samples from pregnant women in groups A and B before and after LT4 treatment, track thyroid function indicators such as TSH, FT4, TPOAb before and after treatment in the three groups of pregnant women, and record maternal and fetal nutritional development.
- ③ Pregnancy outcomes: Track and follow up maternal and fetal outcomes, including the incidence and mode of delivery of adverse pregnancy outcomes such as miscarriage, premature birth, gestational hypertension, gestational diabetes, premature rupture of membranes, fetal growth restriction, macrosomia, intrapartum blood loss, neonatal sex, weight, head circumference, height, Apgar score, thyroid disease, etc.
- ④ Statistical methods: SPSS 26.0 software was used for statistical analysis; continuous data were described by (mean  $\pm$  standard deviation), and count data were expressed by frequency and rate; two independent samples that met normal distribution and homogeneity of variance were analyzed by t test and corrected t test; comparison of binary data between two independent samples of count data was analyzed by X test and corrected X test; P < 0.05 was considered statistically significant.

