## Result

(1) There was no significant difference between the disease group and the control group in general conditions such as age, BMI, gestational age, etc.; (2) The disease group had higher TC and LDL levels than the control group, as well as high-sensitivity C-reactive protein (hsCRP) levels, Th17, Th17/Treg ratio was significantly higher than that of the control group, and the percentages of Treg and IL-10 were significantly lower than the control group; (3) TSH, hsCRP, Th17, Th17/Treg ratio, and TNF- $\alpha$  in the disease group after LT4 intervention were significantly higher decreased, and FT4, Treg, and IL-10 increased significantly; (4) The incidence of SIBO in the disease group was higher than that in the control group, and the incidence of SIBO in the disease group after intervention was lower than before intervention; (5) Compared with the HA group, The TSH level of the HB group was lower and the IL-10 level was higher, but there was no significant difference in the levels of blood lipids such as TC, TG, HDL, LDL and other inflammatory factors such as hsCRP and IL-2 between the two groups; (6) Correlation analysis in pregnant women with normal-high TSH values and positive TPOAb: TSH is positively correlated with hsCRP, negatively correlated with Treg proportion, TPOAb is positively correlated with TNF- $\alpha$ ; IL-10 levels are negatively correlated with IL-2 and IL-4 levels; TC is positively correlated with hsCRP.

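### Before/after stool and non-thyroid blood sampling is planned only in the LT4 groups and no paired test is listed, so marker and SIBO changes drawn from those samples cannot show an LT4 effect

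*Combined protocol and SAP*

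**What the plan says.** The design has two LT4 groups, A (25 ug) and B (50 ug), of 100 women each, and an untreated group C of 200 (1. Research content). Allocation is not described as random.

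Under 2. Research steps, item 2 has two sampling clauses. The first is "Collect blood and stool samples from pregnant women in groups A and B before and after LT4 treatment". The second is "track thyroid function indicators such as TSH, FT4, TPOAb before and after treatment in the three groups of pregnant women". Item 1 also records serological indicators beyond thyroid function for all women at grouping, with no repeat stated. Neither section names a cytokine, hsCRP, Th17/Treg or SIBO measurement.

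For continuous data item 4 says "two independent samples that met normal distribution and homogeneity of variance were analyzed by t test and corrected t test". For binary data it gives chi-square tests for two independent samples. It lists no paired test, no test of change and no adjustment.

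The Result section reports before/after findings. Item 3 describes TSH, hsCRP, Th17, Th17/Treg and TNF-alpha as decreased, "in the disease group after LT4 intervention were significantly higher decreased, and FT4, Treg, and IL-10 increased significantly". Item 4 adds that "the incidence of SIBO in the disease group after intervention was lower than before intervention". A control group appears only in comparisons of level, for example "as well as high-sensitivity C-reactive protein (hsCRP) levels, Th17, Th17/Treg ratio was significantly higher than that of the control group" and "The incidence of SIBO in the disease group was higher than that in the control group". Item 5 compares two groups called HA and HB: "The TSH level of the HB group was lower and the IL-10 level was higher".

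**The concern.** A change from before to after treatment in treated women combines the drug effect with everything else that happens as pregnancy advances. A concurrent untreated series would separate the two. Item 2 names A and B for the study samples and then all three groups for thyroid function, so a repeat marker or SIBO series in group C is not planned.

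The Result section words the immune-marker and SIBO changes as following LT4 intervention, and a reader could easily take them as drug effects. Without an untreated comparator, an inactive drug could also produce significant changes.

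Two further problems do not depend on where the Result data came from. The plan has no valid test for any before/after change. It also has thyroid values in group C but plans no adjusted comparison with them, while the Result section reports TSH and FT4 after LT4 only as changes from before. Entry requires TSH of at least 2.5 mIU/L, so TSH can fall on retest in women who take nothing.

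**Working it through.** The documents give no SD, drift, correlation, marker sample size or power, so there is no stated figure to reproduce. From the documents: groups of 100, 100 and 200, and P < 0.05 (two-sided assumed). All else below is assumed and shown as a range.

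**1. Independent t test on paired data.** The test uses a standard error of SD × √(2/n). The true one is SD × √(2(1−r)/n). With no change it therefore rejects when |Z| > t/√(1−r). At n=100 per time point, t(0.975, 198) = 1.972:

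| r | t/√(1−r) | Rejection with no change |
|---|---|---|
| 0.3 | 2.357 | 1.8% |
| 0.5 | 2.789 | 0.5% |
| 0.7 | 3.600 | 0.03% |

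The nominal rate is 5%.

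**2. What a paired test would call significant.** The threshold is t(0.975, n−1)/√n in SD of change: 1.984/10 = 0.198 at n=100, and 1.972/14.14 = 0.139 at n=200 (A and B pooled). For SIBO by McNemar, if 20/30/40 women change status, a net fall of 10/12/14 women is enough (exact P = 0.041/0.043/0.038). That is 10/12/14 percentage points at n=100 and 5/6/7 at n=200.

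**3. Inactive drug with drift.** Drift d is in SD of change. The paired column uses the noncentral t with noncentrality d√n. The independent column uses |Z + d√n| > t/√(1−r) with r = 0.5.

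| n | d | Paired t significant | Independent t significant |
|---|---|---|---|
| 100 | 0.1 | 17% | 4% |
| 100 | 0.2 | 51% | 22% |
| 100 | 0.3 | 84% | 58% |
| 200 | 0.1 | 29% | 9% |
| 200 | 0.2 | 80% | 52% |
| 200 | 0.3 | 99% | 93% |

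Drift must run in the reported direction to produce the reported result. Opposite drift would hide an effect.

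**4. Untreated fall in TSH on retest.** Assume log-normal TSH with median 1.2/1.5/2.0 mIU/L, log-SD 0.5/0.6, retest correlation 0.5/0.7/0.85, and entry at 2.5 to 4.0. Over these 18 combinations the expected untreated fall is 0.06 to 0.91 mIU/L. In the middle case (1.5, 0.5, 0.7) the mean goes from 3.03 to 2.61. On the raw scale the expected z is below −1.96 in 12 of 18 combinations at n=100 and 15 of 18 at n=200.

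**5. What a comparison with group C can detect.** At 80% power the detectable difference is (1.960 + 0.842) × √(1/100 + 1/n_C), in SD of the follow-up value. Baseline adjustment at an assumed correlation of 0.5 multiplies it by √(1 − 0.25) = 0.866.

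| Group C women used | Unadjusted | Adjusted |
|---|---|---|
| 200 | 0.34 | 0.30 |
| 100 | 0.40 | 0.34 |
| 50 | 0.49 | 0.42 |

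**The case against.** The strongest objection is that the Result data may not come from the item 2 samples. The disease, control, HA and HB groups appear nowhere in the design sections, and A, B and C all meet the disease entry criteria. The Result section also gives marker and SIBO levels for a control group, so its data may extend beyond what item 2 describes. This stands, and it makes the uncontrolled-change point conditional. The missing paired test and the unused group C comparison are unaffected.

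A reader might infer that group C gives no repeat blood at all. The documents do not support that. Tracking thyroid function before and after in three groups requires blood from group C, and item 1 allows other baseline serology there. The gap is repeat stool and repeat non-thyroid assays.

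A reader might also take the IL-10 difference between HA and HB as comparative support for that marker. Result item 5 does not say when the two groups were measured, so a baseline difference would read the same. No marker gains clear support from it.

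It is also fair that the independent t test is conservative on paired data, so the missing paired test does not explain significant findings. It is still the wrong test. Finally, the Result section states no causal conclusion and prints no P values, so the illustration cannot be compared with reported ones.

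**Conclusion.** The point holds in a limited form and should be fixed. Two parts are unconditional. The listed tests do not suit before/after data, with a true size of about 1.8 to 0.03% for assumed correlations of 0.3 to 0.7. The thyroid values in group C are also left out of any adjusted comparison, although selection on TSH makes an untreated fall likely.

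The third part depends on the Result markers coming from the item 2 samples. If they do, the changes are within-group changes with no untreated comparator. Modest assumed drift of 0.1 to 0.3 SD of change would then make an inactive drug look significant in 17 to 84% of cases at n=100 and 29 to 99% at n=200. The size and direction of any drift, and the marker sample sizes, are not in the documents.

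None of this shows that LT4 has no effect on these markers, or that drift occurred. It shows only that such data cannot tell the two apart. The absence of an untreated marker series does not affect the A-versus-B dose contrast or the pregnancy outcomes.

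**What to change.** 1. **Markers and SIBO.** Analyse before/after changes with paired methods (paired t test, McNemar). Report them as descriptive and draw no conclusion about LT4 versus no LT4. Make any comparative marker statement as a non-randomised A-versus-B contrast of follow-up values adjusted for baseline.
2. **Thyroid function, as a separate change.** Replace the before/after TSH and FT4 claims with A-minus-C and B-minus-C differences in follow-up value, and analyse TPOAb the same way. Fit one regression per outcome, adjusted for baseline value and the recorded covariates (age, height, weight, pregnancy and delivery history). Compare at similar gestation where sampling dates allow. State how the follow-up time is set in group C, which has no treatment start. Report as non-randomised.
3. **Groups.** Map the disease, control, HA and HB groups to A, B and C, and give the number of women with marker data, so that (1) and (2) can be applied. If a repeat untreated marker series exists, say so; that would resolve the conditional part.

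The cost is SAP and report wording and three regression models on values already tracked, with no new samples or assays. There will be fewer claims about LT4, residual confounding remains, and matching on gestation loses some group C values. As the last table in the working shows, the adjusted detectable difference rises from 0.30 SD with all 200 group C women to 0.42 SD with 50.

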## Feasibility Analysis

Levothyroxine is an effective drug for the treatment of thyroid diseases. It is easily absorbed by the body, has a high utilization rate, and is widely used in clinical practice. The information on the condition of the subjects collected in this study is obtained from routine perinatal care and will not harm their health and rights; the peripheral blood collection in this study is often carried out at the same time as other similar blood test items, without the need for additional blood collection, and the amount of blood collected is small, which causes little harm to the research subjects, and the rest of the samples are collected non-invasively.

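### Thyroid tests are timed by treatment in all three groups, but group C is untreated, so the plan gives no common test dates for comparing follow-up thyroid function

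*Combined protocol and SAP*

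**What the plan says.** Research content sets up three groups. A and B receive LT4, "with 100 cases in each group according to the dose of LT4 of 25ug and 50ug". The third is untreated: "those who did not take LT4 were group C, with 200 cases". Eligible women are those "diagnosed with normal-high TSH and positive TPOAb before 20 weeks of pregnancy", with TSH between 2.5 mIU/L and the upper limit of the reference range.

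Research steps, item 2, gives the measurement rule: TSH, FT4 and TPOAb are to be tracked "before and after treatment in the three groups of pregnant women". Blood and stool sampling, in the same item, is limited to the treated women: "Collect blood and stool samples from pregnant women in groups A and B before and after LT4 treatment". Neither sentence gives a week, a date or an interval.

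Feasibility Analysis adds that "The information on the condition of the subjects collected in this study is obtained from routine perinatal care". Item 4 of Research steps lists t tests and chi-square tests for two independent samples at P < 0.05. It mentions no covariates.

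**The concern.** The rule dates both thyroid tests by an event that group C never has, and no other part of the plan supplies a substitute. The person extracting the data must then choose which two results count for each untreated woman, and nothing makes that choice match the interval used in A and B.

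What is at stake is the purpose of the untreated group. Women enter because their TSH lies in a selected band, so a second value can move without any treatment, through regression to the mean and through advancing gestation. An untreated group followed over the same interval is what separates these movements from an LT4 effect. If the interval differs, part of the untreated movement stays in the treated-minus-untreated difference. The documents themselves treat TSH limits as depending on the stage of pregnancy: the guideline they cite in the background and in Safety Analysis gives 4.0 mIU/L for early pregnancy as an alternative upper limit. The timing of a test is therefore not a formality.

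**Working it through.** The plan states no power, SD, effect size or sample-size derivation, so there is no figure of its own to reproduce. The check is a reading of the text, followed by an account of what a number would require.

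**Step 1. Can the rule be applied?**

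| Group | n | LT4 | Date of the before test | Date of the after test |
|---|---|---|---|---|
| A | 100 | 25 ug | before LT4; week not stated | not stated |
| B | 100 | 50 ug | before LT4; week not stated | not stated |
| C | 200 | none | no anchor | no anchor |

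The rule has no meaning for 200 / (100 + 100 + 200) = 50% of the women. In A and B only the before test has an anchor, since no length of treatment is given.

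**Step 2. Does anything else fix the timing?**

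- Entry: any week before 20, with no matching between groups on gestational week.
- Visits: data come from routine care, and no study schedule is given.
- Recording: gestational week at testing is not named among the basic items in item 1 of Research steps, although that list is not presented as complete.
- Allocation: no randomisation is described, so nothing balances gestational week at entry.
- Analysis: two-sample tests without adjustment.
- Result section: it reports no significant difference in gestational age, but between a disease group and a control group that are not mapped to A, B and C. It does not refer to the interval between tests.

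**Step 3. What would the contrast contain?** Let d be the interval from first to second test, w the gestational week at the first test, and g(w) the mean value of the marker at week w without treatment. Then

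difference in mean change, A minus C = LT4 effect + {[g(wA + dA) − g(wA)] − [g(wC + dC) − g(wC)]} + (difference in regression to the mean).

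If g is a straight line with slope r per week, the term in braces is r × (dA − dC), which is zero when the intervals are equal. If g is curved, it also depends on wA and wC, so equal intervals are not quite enough and the week at entry matters too. Regression to the mean cancels only if the first test has the same role in every group (for example, the qualifying test) and the interval is the same. The same expression applies to B minus C, and to A minus B.

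**Step 4. Can this be sized?** For 100 versus 200 women, SE = SD × sqrt(1/100 + 1/200) = 0.122 SD. For A versus B, SE = SD × sqrt(1/100 + 1/100) = 0.141 SD. A timing shift b distorts the A–C test according to b / (0.122 SD). The documents give neither r, dA, dB nor dC, from which b would follow, nor the SD of follow-up values or of change. Any error rate would be built wholly on assumed inputs.

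**The case against.** Four points can be made for the plan.

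- **An unstated interval is not an unequal one.** All data come from routine perinatal care, and one clinic calendar could bring the three groups to testing at similar weeks. This stands: similar timing is plausible. It is not assured, because no rule requires it.
- **Item 2 says the markers are tracked, not compared.** No test is assigned to change in TSH, FT4 or TPOAb, and no A–C contrast is named. This stands as a matter of wording. The contrast is inferred from the three-group design, the two-sample tests and the aim of assessing clinical efficacy; without it, an untreated group of 200 has no evident use.
- **The title and aim stress different doses, so A versus B is the main question, and both groups have a real before and after.** This stands in part. The second test has no stated time in A or B either, so the dose contrast is also exposed.
- **Pregnancy outcomes are listed separately and are untouched.** This stands. The point concerns the thyroid markers only, and no primary endpoint is named.

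Two stronger readings are tempting. A reader might infer that treated-minus-untreated differences in this study do mix LT4 with gestational age. The documents show only that nothing prevents it. A reader might also derive an inflated false-positive rate, taking the SD from the width of the TSH entry band and assuming a weekly drift and a gap between groups. That fails on each input. Eligibility truncates entry values but not follow-up values or changes. The 4.0 mIU/L ceiling is the guideline's early-pregnancy figure, whereas the inclusion criterion says only the upper limit of the reference range. Neither the drift nor the gap appears in the documents.

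**Conclusion.** The point holds as a defect in the measurement rule, with a risk of bias that follows from it. The rule cannot be applied to 200 of 400 women, and no common follow-up time is set for the other 200. If timing differs between groups, unadjusted t tests would attribute gestational change and regression to the mean to LT4.

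The existence of the gap rests on the text alone. Its consequence rests on two conditions: that follow-up thyroid values are compared between groups, which the design implies but the plan does not state, and that test timing differs in practice, which the documents neither show nor exclude. The bias could be small if all groups were tested at similar weeks. Its size and direction cannot be given. The plan should be changed because the correction is cheap and the untreated comparison cannot be interpreted with confidence without it.

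**What to change.** Replace the timing rule in item 2 of Research steps with wording such as: *Thyroid function is measured at entry and again in one follow-up window, counted from entry and identical for groups A, B and C; gestational week is recorded at both tests.* Entry should be defined by the same event in all three groups. The sponsor should choose the window from existing routine visits. Where data have already been collected, the same rule can select tests from the records.

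In item 4, compare follow-up values between groups adjusted for the entry value and for gestational week at entry. With a common window, the week at follow-up is close to the week at entry plus a fixed interval, so a second gestational covariate is not needed. This adjustment does not remove other differences between groups that were not randomised.

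The cost is one replaced sentence, one added line of analysis, and covariates that the antenatal record should hold. Some results will fall outside the window and must be set aside or handled in a sensitivity analysis. No dose, group size or significance level changes.
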